4.1.2 Secondary endpoints

- Evolution of daily extravascular lung water index (EVLWi), cardiac index, global end-diastolic volume index, pulmonary vascular permeability index, measured by transpulmonary thermodilution during 7 days.
- Overall survival at 30 days
- Mortality rate in ICU, in hospital
- Rate of withdraw or withhold life-sustaining treatments decision at Day 30
- Vascular leak:
 - Daily weight until D7 (% of D1)
 - Daily fluid balance until D7
 - Evolution of albuminemia until D7
- Pulmonary recovery:
 - Duration of mechanical ventilation (MV) and MV free days at D30
 - Ventilator-free survival (proportion of participants alive and off invasive mechanical ventilation) at D30
 - PaO₂/FiO₂ and Murray ARDS severity score over 15 days
 - Evolution of pulmonary SOFA score over 15 days
 - Evolution of radiological Weinberg score over 30 days, analysed by a specialized radiologist, blinded for the treatment group
 - Rate of rescue therapy with VV-ECMO
- Evolution of daily sequential organ failure score (SOFA) and organ failure (one or more SOFA sub-score ≥3) failure free days at D15
- Hemodynamic parameters
 - systolic, diastolic, mean blood pressure, heart rate twice a day during 7 days
 - lactate clearance, measured once a day during 7 days
 - catecholamine-free days at D30
- Duration of renal replacement therapy (RRT), and RRT free days at D30
- Nature and frequency of adverse events
- Evolution of FX06 concentration from H0 to H1, measured at time 0 (before FX06 application) and after 5, 15, 30, 60 min
- PK/PD analysis will be performed from those dosages, with a reduction of EVLWi of more than 30% before and 3 hours after injection as primary PD endpoint at day 2
- Immunogenicity of the drug will be tested at day 7, according to manufacturer's procedure (cf 5.7)

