 - Positive end-expiratory pressure (PEEP)
 - Plateau pressure
 - FiO₂
 - Level of catecholamines: inotrope score, calculated as IS= dose of dubutamine (µg/kg/min)+ 100 x [dose of norepinephrine (µg/kg/min) + dose of epinephrine (µg/kg/min)] [16]
 - Supplementation by hydrocortisone Y/N
 - Biological exams :

- Arterial blood gases
 - Haematology (blood count)
 - Ionogram, renal and hepatic markers
 - serum glucose, CRP, LDH, NT-pro-BNP, procalcitonin, troponin
 - Coagulation tests: PT ratio, aPTT, Fibrinogenemia, D-Dimers
 - Albuminemia
 - ECG
 - SOFA score
 - RRT or not
 - Chest x-ray
 - Trans-thoracic echocardiography
- Assessment of transpulmonary thermodilution (TPT) parameters. **One measurement will be made before administration of the treatment [7]. All parameters will be evaluated in supine position. Parameters recorded will be: Extra-vascular lung water index, Global end-diastolic volume index, pulmonary vascular permeability index, and cardiac index.** Central venous and arterial lines used for the routine care of the patient will be compatible with TPT systems (either PICCO, Getinge, Germany or EV1000, Edwards Lifesciences, US).
- Treatment
 - Administration by IV perfusion 400mg FX06 intravenously or placebo as a two-time bolus within 10 minutes interval)
 - Administration as soon as possible after randomization, but no longer than 12 hours.
- Pharmacokinetic study: Additional 1 ml blood sample will be taken at time 0 (before FX06 application) and after 5, 15, 30, 60 min. Because FX06 in blood is quickly degraded by endopeptidases, the following sampling procedure should be followed: 1 ml blood to be collected into tubes containing Li-heparin, mixed by inversion 10 times, and then 0.8 ml of this blood to be transferred to test tubes containing 0.08 ml of 0.88 M HCl. It is critical that blood is being transferred to acid within 2 min of collection. The tubes are closed, the acidified blood samples will be mixed by inversion 10 times, and then processed to plasma by centrifugation (2500g; 10 min). Acidified plasma samples will be stored at a temperature of less than -20°C. FX06 dosage will be processed according by F4-Pharma, according to its dedicated procedure. Alternatively, pharmacokinetic study may be performed every other day of treatment (D1 to D5).

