12 STATISTICAL ASPECTS

12.1 Description of statistical methods to be used including the timetable for the planned interim analyses

The statistical analysis will be performed by a biostatistician of the Clinical Research Unit of Pitié-Salpêtrière Hospital, under the responsibility of [name] [name].

Statistical analyses will be performed with the SAS® or R software with the most recent version at the time of the analysis.

Descriptive analysis will always be overall and by treatment group.

Unless specially mentioned, comparative analysis between groups will be systematically performed without adjustment (univariate analysis);

Flow chart

A flow chart according to the CONSORT recommendations will describe the recruitment and the follow-up of all study population.

Study population

The primary analysis of efficacy endpoints will be performed on all randomized patients for whom a baseline evaluation is available, on an intention-to-treat (ITT) population. All patients will therefore be analyzed in their initial randomization groups.

The safety set is defined as all randomized patients having received at least one dose of study treatment. Safety endpoints will be analyzed on the safety set.

Descriptive analysis

Qualitative variables will be described with frequency and percentage distributions, and quantitative variables with median, interquartile range, minimum and maximum values, mean and standard deviation.

Censored data will be described by Kaplan-Meier estimation or cumulative incidence function, with rate at D7 and D30 with 95% confidence interval.

Baseline characteristics

Demographical, clinical, biological and treatment characteristics will be described.

Primary analysis

The primary analysis will be performed in the intention to treat population.

The primary outcome is the change in EVLWi between D1 and day 7. These changes will be compared between both arms using analysis of covariance (ANCOVA), adjusted for the D1 EVLWi. This is fully equivalent to comparing EVLWi scores at D7 adjusted for the baseline EVLWi. Results will be expressed in terms of adjusted mean changes, with their 95% confidence interval. The unadjusted supportive analysis will be carried out by comparing EVLWi at day 7 between the two arms with a t test.

If the distribution of EVLWi is clearly incompatible with the ANCOVA or t test assumptions, then these analyses will be conducted on the ranks.

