For patients dying before 7 days, the last thermodilution data will be retained for the primary analyses. If the patient's condition no longer warrants the presence of the transpulmonary thermodilution systems, then the catheter is removed before 7 days. In this case, the measurement of EVLWi can no longer be made, the last thermodilution data will be retained for the primary analyses. A sensitivity excluding those patients will be performed for analysing the primary endpoint.

Secondary analyses

For safety, the types and severity of AEs and SAEs will be described as frequency and percent by treatment arm. Fisher's exact tests will be used to compare the two treatment arms in terms of proportion of patients with death (all cause), at least one AE/SAE, at least one SAE. The number of these events (except death) will be compared between arms by Poisson regression.

Overall survival at D30 will be compared between the two groups using a logrank test.

The evolution of EVLWi during 7 days and other longitudinal repeated efficacy secondary outcomes will be compared between the two groups using a linear mixed effect model to take into account within subject correlation. If the model assumptions (normally distributed residuals with constant variance) is debatable, these analyses will be conducted on the ranks.

For other efficacy secondary outcomes, data will be described graphically and compared between arms by:

- chi2 test or fisher test for binary outcomes;
t-test or wilcoxon rank-sum test for quantitative variables.

Subgroups analyses will be performed according to :

- Presence of VV-ECMO at baseline (Yes/No)
- EVLWi at baseline (>10 ml/kg) (Yes/ No)

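### The protocol's no-adjustment rule leaves longitudinal secondary outcomes unadjusted for their own D1 value, unlike the primary EVLWi analysis, at a cost in precision and consistency

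*Protocol*

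**What the plan says.** Section 12.1 opens with a general rule: "Unless specially mentioned, comparative analysis between groups will be systematically performed without adjustment (univariate analysis". The one baseline adjustment it then mentions is in the primary analysis, where the D1-to-D7 change in EVLWi is compared "using analysis of covariance (ANCOVA), adjusted for the D1 EVLWi".

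Under Secondary analyses, the 7-day course of EVLWi and "other longitudinal repeated efficacy secondary outcomes will be compared between the two groups using a linear mixed effect model". The stated purpose of that model is "to take into account within subject correlation". The text gives no baseline term, does not say whether D1 enters as a response, and names no contrast.

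The baseline values exist for most of these outcomes. Section 5.1 (D1) asks for one thermodilution measurement before treatment, covering EVLWi, global end-diastolic volume index, pulmonary vascular permeability index and cardiac index. It also lists arterial pressure, heart rate, blood gases, FiO2, albumin and SOFA. The chronology table in 5.6 marks EVLWi only from D2, but 5.1 and the definition of the primary endpoint both require the D1 value.

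Two longitudinal outcomes are different. Section 4.1.2 already expresses weight as a percentage of D1, and daily fluid balance has no D1 entry in 5.1 or 5.6.

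**The concern.** The same EVLWi measurements are analysed under two rules: adjusted for D1 in the primary analysis, and by default unadjusted in the first-listed secondary endpoint. No reason is given.

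With 25 patients per arm, chance differences at D1 can be appreciable. An analysis of follow-up levels that ignores D1 carries such a difference into the estimate in proportion to the correlation. A simple change from D1 over-corrects for it when the correlation is below 1. Conditioning on D1 avoids both.

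At stake is the usefulness of the repeated physiological measures, which are the main supporting evidence in a 50-patient phase IIa trial. A secondary EVLWi result could also differ from the primary partly because of how baseline was handled.

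**Working it through.** **Inputs from section 12.2.** SD 5 ml/kg, baseline mean 13.4, decrease 30%, 25 per arm, two-sided 5%. The difference is 0.30 × 13.4 = 4.02 ml/kg, so d = 4.02/5 = 0.804.

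**Reproducing the plan's figure.** n per arm = 2 × ((1.960 + 0.842)/0.804)² = 24.3, rounded up to 25. The stated sample size reproduces. Exact (noncentral t) power at 25 per arm is 79.5%; the normal approximation gives 81.1%.

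**Assumption.** The protocol gives no correlation rho between D1 and follow-up, so I use 0.3, 0.5 and 0.7.

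**Single-day approximation.** With equal variances at both times, the variance of the arm difference relative to a raw follow-up comparison is:
- follow-up only: 1
- change from D1: 2(1 − rho)
- D1-adjusted: 1 − rho²

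For rho strictly between 0 and 1, 1 − rho² is below 1. It is also below 2(1 − rho), because 1 − rho² = (1 − rho)(1 + rho) and 1 + rho < 2. So for a given contrast the direction of the gain does not depend on the assumed rho; only its size does.

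Power by noncentral t with d divided by the square root of the factor (48 df; 47 for the adjusted analysis):

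| rho | factors (change; adjusted) | follow-up only | change from D1 | D1-adjusted |
|---|---|---|---|---|
| 0.3 | 1.40; 0.91 | 79.5% | 65% | 83% |
| 0.5 | 1.00; 0.75 | 79.5% | 79.5% | 89.5% |
| 0.7 | 0.60; 0.51 | 79.5% | 95% | 97% |

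For a smaller effect of 0.5 SD at rho 0.5, the three figures are 41%, 41% and 52%.

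**Mean arm difference over D2–D7.** I assume compound symmetry, SD 5 and complete data. The variance of a patient's six-day mean is 25(1 + 5·rho)/6. Conditioning on D1 removes 25·rho². The SE of the arm difference is the square root of (2/25) × variance.

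| rho | variance, unadjusted | variance, adjusted | SE, unadjusted | SE, adjusted | excess |
|---|---|---|---|---|---|
| 0.3 | 10.42 | 8.17 | 0.91 | 0.81 | 13% |
| 0.5 | 14.58 | 8.33 | 1.08 | 0.82 | 32% |
| 0.7 | 18.75 | 6.50 | 1.22 | 0.72 | 70% |

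**Disagreement with the primary.** Simulation of 5,000 trials per scenario used the same structure with the effect building linearly to 4.02 at D7. The share of trials in which significance differs from the D7 ANCOVA was:

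| Secondary analysis | rho 0.5 | rho 0.7 |
|---|---|---|
| D2–D7 mean, unadjusted | 38% | 51% |
| D2–D7 mean, D1-adjusted | 18% | 10% |
| D7 minus D1 | 13% | 3% |

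Both the baseline handling and the choice of contrast matter.

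**The case against.** The strongest reply is that the protocol does not fix the model. Describing the evolution of EVLWi over 7 days suggests that D1 may be one of the responses. A treatment-by-day test would then already use baseline. In that case the loss can be small: at rho 0.7 the change contrast has 95% power against 97%. If the effect builds linearly, a treatment-by-day slope test is at least as powerful as the D7 ANCOVA (normal approximation: 85%, 94% and 99.6% at rho 0.3, 0.5 and 0.7, against 85%, 91% and 98%). Details of this kind commonly sit in a statistical analysis plan, which is not shown. The reference to univariate analysis might also be meant only to exclude multivariable covariate models.

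Much of this stands, and it limits the claim. It does not remove it. The blanket rule is written in the protocol, so an analysis plan that follows it would leave D1 out as a covariate, and nothing secures the favourable form of the model.

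A reader might infer three stronger things that the document does not support:
- **That every secondary test loses precision.** This depends on the unstated contrast. Weight is already relative to D1, fluid balance has no D1 value, and outcomes such as ventilator-free survival or the VV-ECMO rate are not repeated measures.
- **That baseline handling alone would explain a conflict with the primary.** A 7-day course and a D7 value are different quantities, and carrying forward the last thermodilution value is stated only for the primary analyses.
- **That the unadjusted tests are biased or inflate the type I error.** Under randomisation they do neither.

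**Conclusion.** The point holds as a weakness of efficiency and consistency in the secondary analyses. The rule in 12.1, read with a mixed model that mentions no baseline term, leaves longitudinal outcomes unadjusted for a D1 value that is collected, while the primary analysis of the same EVLWi measurements adjusts for it.

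At a single day with the plan's EVLWi inputs, D1 adjustment gains about 4 to 18 points of power over follow-up only across rho 0.3 to 0.7 (79.5% to 83%, and 79.5% to 97%). Over change from D1 it gains about 18 points at rho 0.3, falling to about 2 at 0.7. For an unadjusted D2–D7 mean difference, the SE is 13% to 70% larger than it need be.

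These sizes rest on an assumed rho, compound symmetry for the D2–D7 figures, complete data and the primary endpoint's effect size. No secondary endpoint is formally powered, and the primary analysis and its sample size are unaffected.

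**What to change.** In section 12.1, exempt from the no-adjustment rule each longitudinal outcome that has a pre-treatment D1 value and is not already expressed relative to D1: EVLWi, cardiac index, global end-diastolic volume index, pulmonary vascular permeability index, PaO2/FiO2, SOFA, albumin, blood pressure and heart rate. Leave out fluid balance, and weight as a percentage of D1.

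For these outcomes, specify either post-D1 values as responses with D1 as a covariate, or D1 as a response with a common baseline mean across arms. The second form also handles a missing D1 value. Include treatment, day and treatment-by-day terms, name the contrast, and report it with its 95% confidence interval. For EVLWi the contrast should be the D7 difference, so that it lines up with the primary.

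The cost is a few lines of protocol or analysis-plan wording and one extra term per model, with no new data. Section 12.6 allows justified changes before the analysis begins. Disagreement with the primary remains possible because carry-forward applies only there; the report should say so.

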- The mortality of those severe forms of the disease is very high, around 60% [3], justifying an urgent research to find an appropriate treatment.
 - The level of vascular leak is an independent predictor of mortality during ARDS.
-

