12.2 Calculation hypotheses for the number of participants required and the result

According to previous studies, standard deviation for EVLWi during ARDS is around 5 ml/kg predicted body weight [2]. Assuming a baseline mean of EVLWi of 13.4 and a 30% decrease in EVLWi in FX06 treated patients compared to controls at Day 7, **for 80% power and an overall 5% two-sided α -risk**, the required sample size is **25 patients per group**.

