12.3 Anticipated level of statistical significance

Analyses will be performed with a two-sided alpha risk of 5%.

12.4 Statistical criteria for termination of the study.

No interim analysis will be performed.

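### Ventilation and dialysis durations are tested between arms with no rule for deaths, so more or earlier death in one arm can read as faster recovery

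*Protocol*

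**What the plan says.** Protocol section 4.1.2 lists three secondary endpoints that matter here: "Duration of mechanical ventilation (MV) and MV free days at D30", "Duration of renal replacement therapy (RRT), and RRT free days at D30" and "Rate of rescue therapy with VV-ECMO". None states how death enters, and the third names no at-risk population.

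Section 12.1 gives specific methods for safety, for overall survival (logrank) and for repeated measurements (mixed model). All other efficacy outcomes go to a chi-square or Fisher test if binary, or to a "t-test or wilcoxon rank-sum test for quantitative variables". The efficacy set is all randomised patients with a baseline evaluation. Cumulative incidence functions appear only under descriptive analysis. The one rule for deaths, keeping the last thermodilution value, concerns EVLWi.

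On mortality, section 2.4 says: "The mortality of those severe forms of the disease is very high, around 60% [3". On ECMO, section 12.1 plans a subgroup by "Presence of VV-ECMO at baseline (Yes/No", section 5.1 records VV-ECMO at D1, and section 6.2 does not exclude it. Patients already on VV-ECMO can therefore be enrolled.

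**The concern.** Time on a ventilator ends in two ways: the patient is liberated or dies. A t-test or rank test on raw duration treats both alike. Someone who dies ventilated on D3 contributes about three days and ranks better than a survivor extubated on D14. If the drug increased deaths or brought them forward, mean ventilation time would fall and the test could declare pulmonary recovery improved. Dialysis time works the same way for patients who die while receiving RRT. With mortality near 60%, deaths are a large part of the data.

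The VV-ECMO rescue rate has two weaker forms of the problem. A patient who dies first counts as not rescued. A patient on VV-ECMO at entry cannot newly be rescued by it, yet stays in the denominator.

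This goes beyond detail normally left to a statistical analysis plan. The protocol itself assigns the tests, and an analysis plan that follows it inherits the problem.

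**Working it through.** **The plan's own figure.** The protocol gives no figure for these endpoints. Its sample size (section 12.2) supplies the arm size used below. With a difference of 0.30 × 13.4 = 4.02, SD 5, "for 80% power and an overall 5% two-sided" error:

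n = 2 × (1.960 + 0.842)² × 5² / 4.02² = 24.3, so 25 per group. It reproduces.

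**Constant-hazard example.** Assumed, because the documents give only the 60%: extubation hazard 0.045/day in both arms; hazard of death on the ventilator 0.05/day (control) v 0.10/day (drug); follow-up 30 days. Let λ be the sum of the two hazards.

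- Mean MV duration = (1 − e^(−30λ))/λ. Control, λ = 0.095: 0.942/0.095 = 9.9 days. Drug, λ = 0.145: 0.987/0.145 = 6.8 days.
- Deaths on the ventilator by D30 = (death hazard/λ) × (1 − e^(−30λ)). Control: 0.526 × 0.942 = 49.6%. Drug: 0.690 × 0.987 = 68.1%.

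The drug arm has more deaths and no better extubation, yet looks about three days better. Simulating 25 v 25 patients in runs of 3,000 to 6,000 trials, the share in which the Wilcoxon test significantly favours the harmful arm (nominal 2.5%) is:

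| Death hazard, control v drug | Raw MV duration | MV-free days, death = 0 |
|---|---|---|
| 0.05 v 0.05 | about 2.7% | about 2.5% |
| 0.05 v 0.10 | 22-25% | under 1% |
| 0.045 v 0.07 | 9-11% | under 1% |

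**A different model.** Extubation time lognormal (median 14 days, log-SD 0.5) in both arms; patients who die are ventilated until death; control death-time scale 12 days; 3,000 trials per row.

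| Mortality, control v drug | Drug-arm death timing | Mean difference in MV days | Wilcoxon favours drug | MV-free days favour drug |
|---|---|---|---|---|
| 60% v 60% | same | 0.0 | 2.3% | 2.5% |
| 60% v 60% | earlier (scale 6) | −2.1 | 15.3% | 2.4% |
| 60% v 80% | same | −1.2 | 7.2% | 0.0% |
| 60% v 80% | earlier (scale 6) | −4.0 | 49.8% | 0.1% |

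The t-test behaves alike (2.5%, 15.5%, 6.9%, 48.1%).

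**Check on death timing.** Section 10.3.2.1 cites a cohort in which fewer than 25% of deaths fell in the first 5 days. In the constant-hazard example the share is (1 − e^(−5λ))/(1 − e^(−30λ)): 0.378/0.942 = 40% in control and 0.516/0.987 = 52% in the drug arm, so deaths come earlier than the protocol's own source suggests. With Weibull death times that put 13-23% of control deaths by D5 and the death hazard still doubled, false benefit is 15-18%; with a lognormal extubation time as well, 23-29%.

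**VV-ECMO rescue.** Assume a 30% rescue risk in those not yet on ECMO, equal in both arms.

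- Denominator: with 20% v 40% on ECMO at entry, the crude rates are 0.30 × 0.80 = 24% v 0.30 × 0.60 = 18%. Under simple 25 + 25 randomisation, a gap of 5 or more patients on ECMO at entry, in either direction, has probability 11%, 16% or 19% at a prevalence of 20%, 30% or 40%.
- Death first: with an equal ECMO hazard of 0.02/day and a death hazard of 0.03 v 0.06/day, crude D30 rescue is 0.40 × (1 − e^(−1.5)) = 31.1% v 0.25 × (1 − e^(−2.4)) = 22.7%. VV-ECMO or death by D30 is 1 − e^(−1.5) = 77.7% v 1 − e^(−2.4) = 90.9%, which points the right way.

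RRT duration was not simulated. The direction follows from the same reasoning; no size is claimed.

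**The case against.** **The durations do not stand alone.** This is the strongest point. Section 4.1.2 pairs each duration with its free-days and lists ventilator-free survival, which does count death. Overall survival has a logrank test and all-cause death a Fisher test. In 3,000 simulated trials of the 0.05 v 0.10 example, among those with falsely shorter ventilation the drug arm had more deaths on the ventilator in 91% and worse ventilator-free survival in 79%. A reader might infer that the durations are the plan's main evidence for pulmonary recovery or for less dialysis; the endpoint list does not support that. What stands is that the companions usually contradict a false signal but do not repair the test that produces it. The free-day endpoints protect only if death scores 0, which the protocol does not state.

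**ECMO at entry.** A reader might infer that enrolling patients already on VV-ECMO builds in a benefit for the drug. It does not: under 1:1 randomisation they are balanced in expectation, so they dilute the comparison and add chance imbalance in either direction. The text also leaves open whether such a patient might be coded as rescued, and whether the planned subgroup covers this outcome. Counting a patient who dies first as not rescued gives, under complete follow-up, the competing-risk cumulative incidence. That is a legitimate quantity, but it has to be read beside mortality.

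**Size.** The false-benefit rates rest on assumed hazards, and the simplest example places deaths earlier than the protocol's cited cohort. This stands, and it limits what may be claimed about magnitude.

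**Conclusion.** The point holds for raw MV duration and, by the same reasoning, RRT duration. As written, the protocol tests them with no rule for deaths in a population with about 60% expected mortality, so more or earlier death in one arm can pass as shorter treatment. With the death hazard doubled, false benefit on MV duration is about 22-25% under constant hazards and 15-29% with death timing closer to the cited cohort. With the smaller increase to 0.07/day it is about 10%. All these figures are illustrations. When mortality and its timing are equal there is no inflation.

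One could go further and say that a death on D3 earns the best possible score; it does not, since an earlier death or an earlier extubation scores lower. For VV-ECMO rescue the finding is an undefined at-risk group and a rate that needs mortality beside it, not a systematic bias. These are secondary endpoints. The primary analysis and the 25 per group are unaffected. The change should be made, but it does not threaten the trial's main result.

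**What to change.** In section 12.1:

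1. Make MV-free days and RRT-free days to D30, with death by D30 scored 0, the between-arm tests, alongside the ventilator-free survival already listed.
2. Report raw MV and RRT durations descriptively only, by survival status.
3. For VV-ECMO rescue, take as denominator the patients not on VV-ECMO at D1, and report VV-ECMO or death by D30 beside the crude rate.
4. Optionally, compare time to liberation from MV with death as a competing event, if extubation dates are collected; the visit lists in sections 5.2 and 5.3 do not name them. Do not do this for RRT, because patients not on RRT at randomisation have no such time.

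The cost of items 1 to 3 is wording: free-days, vital status, VV-ECMO rescue and VV-ECMO at D1 are already recorded. The downside is that durations lose their p-value, and free-days mix survival with duration, so the components should be shown beside them.
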